## **Study Overview**

---

This initiative supports a quality improvement effort evaluating the use of strategies (including technology-based decision support, referral to a virtual GDMT team, and general educational tools/resources for clinicians and patients) to improve use of guideline-directed therapeutics known to lower cardiovascular (CV) events among patients with cardiovascular diseases of heart failure, atrial fibrillation and type 2 diabetes (T2D)/ASCVD with a specific focus on underserved populations and those with a history of health care disparities.

## Patient Recruitment

TRANSFORM 	750 (250 HFrEF, 250 HFpEF, 500 Atrial Fibrillation, 250 T2D/ASVCD)
------------------------	---

## Intervention

Patients Randomized – 3 Quality Improvement Arms				
Arm	Duration	Surveys	Primary Outcome	Secondary Outcome
Teaching - CardioSmart Resources + Clinician Education	9 months	Patient perception QOL	GDMT baseline to 9 month change in average composite end-point of receiving the main classes of drugs (50% or higher of target doses for HF) among eligible patients	QOL Individual drug improvements Patient perception Cost/cost effectiveness
Technology - Facilitated Solution (Existing Team)				
Teams - Protocol-Supported Team, (Virtual GDMT Team)				

## List of Abbreviations

ACCF	American College of Cardiology Foundation
ACE-I	Angiotensin-converting enzyme inhibitors
ASCVD	Atherosclerotic Cardiovascular Disease
ARB	Angiotensin II receptor blockers
CV	Cardiovascular
CVD	Cardiovascular Disease
CVRiD	CV Risk in Diabetes
DCR	Diabetes Collaborative Registry
EHR	Electronic Health Record
ESRD	End Stage Renal Disease
ECDP	Expert Consensus Decision Pathway
GDMT	Guideline Directed Medical Therapy
GLP1-RA	Glucagon-like peptide-1 receptor agonists
GPP	Good Pharmacoepidemiology Practice
HF	Heart Failure
LVEF	Left Ventricle Ejection Fraction
SGLT-2I	Sodium glucose cotransporter-2 inhibitors
SI	System Integration
SIM CVRiD	Success in Managing CV Risk in Diabetes
T2D	Type 2 Diabetes
VAD	Ventricular Assist Device

## Rationale and Background

---

TRANSFORM is a Quality Improvement initiative conducted in parallel to the current TRANSFORM CVRiD study and aligned with its goals of using a real-world population study to enable the American College of Cardiology Foundation (“ACCF”) to better identify impactful ways to improve guideline directed medical therapy for patients. TRANSFORM is focused on improving GDMT use in underserved patients and patients with a history of health care disparities who have one or more of the following: heart failure, atrial fibrillation, and ASCVD/Type 2 diabetes.

There is a significant disconnect between increasing availability of effective and safe therapeutics that significantly reduce CV event risk in patients with Heart Failure, T2D and ASCVD, and Atrial Fibrillation—and clear guideline recommendations endorsing these therapies—but very low adoption in clinical practice with the majority of eligible patients that are most likely to benefit from these therapies not receiving them. A high proportion of patients have more than one of these conditions further reducing the chances of receiving optimal guideline directed medical therapy and avoiding the CV events they are designed to prevent.

### *Heart Failure (HF)*

HF is the cardiovascular epidemic of the 21st century, affecting millions of patients worldwide. It is the #1 diagnosis leading to hospitalization among Medicare beneficiaries. In addition to being increasingly prevalent, HF has a poor outlook after initial diagnosis and is associated with poor quality of life (QOL) in affected patients; this not only leads to burden on patients, family and other caregivers, but also on the healthcare system.

Although clinical practice guidelines clearly articulate optimal GDMT for care of patients with HF, implementation of GDMT into the management of such patients has proven to be suboptimal, with most patients under-treated relative to goal therapy.

To evaluate contemporary status of GDMT delivery for HFrEF, the recent Change the Management of Patients with Heart Failure (CHAMP-HF) registry included 3518 patients from 150 primary care and cardiology practices (1,2). The mean age of this cohort was  $66 \pm 13$  years, 29% were female, and mean EF was  $29 \pm 8\%$ , thus representing a very characteristic population of patients with HFrEF. In CHAMP-HF, the investigators found 27%, 33%, and 67% of eligible patients were not prescribed angiotensin converting enzyme inhibitor (ACEI)/angiotensin II receptor blocker (ARB)/angiotensin receptor/neprilysin inhibitor (ARNI), beta-blocker, and mineralocorticoid receptor antagonist (MRA) therapy, respectively. Furthermore, when medications were prescribed, few patients were receiving target doses of ACEI/ARB (17%), ARNI (14%), and beta-blocker (28%); most patients were receiving target doses of MRA therapy (77%). Most notably, among patients eligible for all classes of medication, only 1% were simultaneously receiving target doses of renin-angiotensin system inhibitors (RASi; ACE/ARB/ARNI), beta-blocker, and MRA. Remarkably, little improvement in GDMT was noted over a 6 to 12-month period and (importantly) no use of the newest HFrEF GDMT, sodium glucose cotransporter-2 inhibitors (SGLT2i) was reported.

In HFpEF, the MRA spironolactone could be considered for use based on the TOPCAT trial (America's region). Similarly, the ARBs (based on CHARM-Preserved and I-Preserve) appear to modestly lower HF events in patients with HFpEF. The US FDA has expanded labelling for ARNI to all patients with chronic HF noting that patients with an LVEF below normal are most likely to benefit. This regulatory labelling change was based on the PARAGON-HF trial which showed modest clinical benefits of this therapy when studied against valsartan. The SGLT2i empagliflozin was shown to be beneficial in reducing HF events or cardiovascular death among patients with HF with mildly reduced or preserved EF.

### *Atrial Fibrillation (AF)*

AF, the most common arrhythmia in adults, is a top priority for the TRANSFORM program. The estimated risk of developing atrial fibrillation over a lifetime is 1 in 4, and a diagnosis of atrial fibrillation confers a 5-fold increase in ischemic stroke risk.

Anticoagulation reduces the risk of stroke by 60-70%, which is a benefit that outweighs the risk of bleeding for the majority of patients. The American College of Cardiology (ACC), American Heart Association (AHA), and Heart Rhythm Society (HRS) recommend the use of the CHA2DS2-VASc score to estimate stroke risk and to start an anticoagulant in anyone with a score greater than or equal to 2 in men and greater than or equal to 3 in women. The proportion of patients at elevated stroke risk based on the CHA2DS2-VASc score who receive oral anticoagulation (OAC) therapy is a performance metric used by cardiovascular societies and the Joint Commission to assess the quality of cardiovascular care being delivered. Despite the clear benefits of oral anticoagulation for stroke prophylaxis of atrial fibrillation, only 50-60% of eligible patients receive an anticoagulation prescription.

### *Type 2 Diabetes Mellitus (T2D)*

Over 34 million Americans have T2D and >7 million have established cardiovascular disease. T2D is associated with diminished life expectancy (by up to 6-7 years for an average 60-year-old patient).

Patients with T2D have traditionally been managed with diet/lifestyle optimization, glycemic control, other risk factor control (including of blood pressure, weight, and smoking cessation), statin therapy, and renin-angiotensin-system inhibitors (in select patients). The SGLT2i and the GLP-1RA are 2 classes of antihyperglycemic therapies that have demonstrated clinically important improvements in cardiovascular, kidney, and mortality outcomes among high-risk patients with T2D. Despite their availability and a strong evidentiary base, their uptake in clinical practice remains suboptimal. Even with expanding insurance coverage and accruing clinical practice guideline support (across specialties), recent national data have suggested that only ~10-15% of eligible patients are on 1 of these risk reduction therapies. Innovative strategies are needed to promote optimal care practices among high-risk patients living with T2D.

We designed the TRANSFORM as a US-based multi-center trial with the goal of defining optimal implementation strategies to integrate GDMT across disease states, especially in underserved populations or those with health care disparities historically. The study was designed specifically to capture patients across broad integrated health systems encountering multiple

clinician types. All quality improvement initiatives will be remotely deployed directly to clinicians caring for eligible patients by trained Study Managers.

The lack of effective implementation is in part related to therapeutic inertia and lack of effective clinical care models that promote and incentivize adoption of guideline-directed medical therapies (GDMT). Furthermore, while treatment changes are often exclusively made during clinician encounters, this study attempts to evaluate strategies that target the large time periods spent outside of defined ambulatory care encounters. Clinicians may have multiple competing priorities during these short clinic visits and allowing for sufficient time needed to effectively optimize medical therapies may be challenging within the time-constrained context of such a visit. We will seek to investigate a range of currently available clinician-facing implementation strategies (including patient/clinician education, technology-based support, and facilitated referral to a team [specifically virtual GDMT nurse/pharmacy] to determine the potential of various implementation approaches to rethink the 20-minute office visit more broadly and improve use of GDMT among patients with one or more high-risk cardiovascular conditions.

## Study Design

---

TRANSFORM will enroll patients, especially those in underserved populations and those with health care disparities historically, to address guideline directed medical therapy in one or more of the following disease states: HF, ASCVD/diabetes, and AF.

### **The study will address the following key objectives among patients with Heart Failure Atrial Fibrillation, and/or T2D and ASCVD:**

1. Evaluate strategies to improve adoption of evidence-based CV-risk reduction and disease management therapies for HF, AF, and T2D/ASCVD.

### **The research objectives of this study are outlined below:**

**Multi-faceted Implementation Study:** In this quality improvement initiative, we will test 3 currently available quality improvement strategies designed to improve implementation of the guideline-concordant care for patients with Heart Failure, Atrial Fibrillation, and/or T2D and ASCVD. Across select participating health systems, participants with Heart Failure, Atrial Fibrillation, and/or T2D and ASCVD, will be randomized to 1 of 3 implementation strategies:

- a. **Teaching Based Improvement:** Clinician and Patient Education alone;
- b. **Technology-Facilitated Improvement:** Technology Guided Care to provide suggestions for care optimization + Education; or
- c. **Team Based Improvement:** Referral to a third party virtual GDMT team contracted by study partner Biofourmis for care optimization utilizing the same technology based standardized suggestions + Education.

*Key goals of the study will be to:*

- Evaluate uptake or intensification of guideline-concordant cardiovascular risk lowering therapies

- Understand guideline consistent comprehensive care for patients with co-related cardiovascular conditions, especially in underserved populations or those with health disparities historically
- Understand barriers and drivers to optimal care

**Population:**

**750 total with comorbidity overlap (250 HFrEF, 250 HFpEF, 500 AF, 250 T2D/ASVD)**

*Inclusion criteria:*

1. Age  $\geq 18$  years
2. Personal access to a computer and/or smartphone for app download
3. Heart Failure (reduced and preserved ejection fraction) AND/OR
4. Atrial Fibrillation with CHA2DS2-VASc score greater than or equal to 2 in men and greater than or equal to 3 in women AND/OR
5. T2D and ASCVD, defined as follows:
  - a. Known CAD, prior ACS, or coronary artery revascularization
  - b. Prior TIA/stroke or known carotid or intracerebral atherosclerosis
  - c. Prior PAD including requiring revascularization

*Exclusion criteria:*

- All patients
  - Current or anticipated participation in an interventional clinical trial of a drug/device
  - Currently receiving comfort care or enrolled in hospice
  - Life expectancy <1 year
  - Pregnancy or active breastfeeding
  - Current or anticipated participation in an interventional clinical trial (other than TRANSFORM GDMT)
  - Patients without a clinical encounter within three years of study start date
- Heart Failure patients:
  - History of or plan for heart transplantation or left ventricular assist device
  - Palliative chronic inotropic therapy
  - NYHA Class 4 heart failure
- Atrial Fibrillation patients:
  - Current prescription for OAC
  - Reversible cause of atrial fibrillation, such as post-cardiothoracic surgery or thyrotoxicosis
  - History of ischemic stroke in prior 7 days
  - Transient ischemic attack in prior 3 days
  - Platelet count <70,000/ml
  - Hemoglobin concentration <8g/dl
  - History of or condition associated with increased bleeding risk, such as hemophilia
  - History of mechanical valve replacement
  - Major surgical procedure or trauma within 14 days
  - Clinically significant gastrointestinal bleeding within 8 weeks

- History of intracranial, intraocular, spinal, or atraumatic intra-articular bleeding
- T2D/ASCVD patients with or without HF or AF:
  - Current prescription for SGLT2i and GLP-1RA
  - Current or planned hemodialysis
  - Decompensated end stage liver disease
  - Type 1 diabetes
  - Prior diabetic ketoacidosis
  - Gestational diabetes
  - History of pancreatitis or pancreatic cancer

## **Data Sources**

---

This is a prospective implementation trial in which patients in 4-6 large health systems will be randomized to various quality improvement strategies to optimize cardiovascular guideline directed medical therapy.

In all arms clinician choice will not be restricted and care recommendations will not be mandated. All interventions are clinician-facing, already available in current care, and promote best practice / guideline recommended care. All clinicians will be informed at the start of the study about the various quality improvement interventions from which they can “opt out”. All patients will be requested to provide informed consent to allow for data acquisition and follow-up. Data over 9 months in the 3 quality improvement groups will be mapped to pre-specified data fields, a data extractor (external vendor or study site) will extract the EHR data and may be used to supplement data recorded in the Biofourmis patient management platform. Adverse events (should they occur) will be captured at the clinical site level. Patients reporting adverse events will address these with their providing physician. There is no Data Safety Monitoring Board for this study.

## **Data Analysis**

---

At study completion, a data set across study visits will be provided to the contracted analytic center using a analytic plan developed by the study team.

## **Research Question, Objectives & Aims**

---

The goal of this implementation trial is to evaluate several clinician and patient-facing implementation strategies to increase adherence to guideline recommended care and to increase prescription of evidence-based therapies proven to reduce the risk of cardiovascular outcomes in patients, HF, AF and T2D/ASCVD.

Patients will be randomized to 1 of 3 implementation strategies conducted over 9 months: 1) clinician and patient education; 2) technology + clinician and patient education +; 3) referral to

third party virtual team (GDMT team) contracted by Biofourmis+ clinician and patient education. Patients will be followed for 9-months to evaluate for changes in the % of patients who ever receive new CV risk reduction therapies by type of strategy. We hypothesize that care of patients with HF, AF, and T2D/ASCVD, including underserved populations and those with health care disparities historically, can be effectively and safely optimized with support outside traditional ambulatory care encounters.

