### **Primary Objective**

The primary objective of this multi-faceted implementation trial is to determine the impact, if any, of use of teaching, technology or facilitated referral to a dedicated third party team (virtual GDMT) contracted by Biofourmis on:

**TRANSFORM:** GDMT baseline enrollment to 9 month change in prescription of the main classes of drugs (receiving 50% or higher of target doses for HF patients) for the relevant disease states among eligible patients

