#### **Secondary Objective**

##### TRANSFORM:

1. Difference in patient reported outcome scores specifically;
  - a) Difference in patient reported outcomes on Morisky Medication Adherence Scale (MMAS-4) from baseline, 3 and at 9 months
  - b) Difference in patient reported outcomes on Patient Activation Measure® (PAM) from baseline, 3 and at 9 months
  - c) Difference in patient-reported outcome/KCCQ-12 scores from baseline to 9 months (applicable to HFrEF and HFpEF study cohorts only)

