### **Risk/Benefit Assessment**

---

As study procedures reflect CV medication management via guideline recommendations supported by the clinical judgment of the managing physician, there is no envisioned procedural risk to patients through involvement in the study. No testing, time, risk, or procedures beyond those required for routine care will be imposed. The primary risk associated with this project is the potential for a breach of patient confidentiality. The ACCF has established a robust plan for ensuring appropriate and commercially reasonable physical, technical, and administrative safeguards are in place to mitigate such risks as described in the Quality Control section of this protocol.

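### The hypothesis claims that care can be optimised safely, but none of the protocol's specified outcomes measures harm by arm, so they cannot answer that part

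*Protocol*

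**What the plan says.** Under Research Question, Objectives & Aims, the protocol states the hypothesis that care of patients with HF, AF and T2D/ASCVD "can be effectively and safely optimized with support outside traditional ambulatory care encounters". That is a claim about effect and a claim about safety.

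The Primary Objective is "GDMT baseline enrollment to 9 month change in prescription of the main classes of drugs". The Intervention table lists the secondary outcomes as "QOL Individual drug improvements Patient perception Cost/cost effectiveness". The Secondary Objective section is introduced by "Difference in patient reported outcome scores specifically" and names MMAS-4, PAM and KCCQ-12.

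Adverse events appear in the first Data Sources section, in three statements: "Adverse events (should they occur) will be captured at the clinical site level"; "Patients reporting adverse events will address these with their providing physician"; and "There is no Data Safety Monitoring Board for this study". The Risk/Benefit Assessment says "there is no envisioned procedural risk to patients through involvement in the study" and names a confidentiality breach as the main risk.

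**The concern.** A hypothesis with two parts needs at least one outcome for each. Here the effect part has many and the safety part has none. If prescribing rises in arm B or C, the hypothesis sentence invites the conclusion that care was optimised safely, although no specified outcome could have shown otherwise.

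The claim is not trivial. A successful intervention means more patients on these drug classes and at higher doses. The protocol itself treats them as carrying risk: the exclusion criteria list bleeding history, prior ketoacidosis and pancreatitis, and Rationale for Selection Criteria says the exclusions are there to limit risk and intolerance.

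Site-captured adverse events may not fill the gap, because the arms are not followed with equal intensity. A raw count by arm could mix true differences in harm with differences in how closely patients are watched.

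**Working it through.** **1. Outcomes set against the safety claim**

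| Protocol section | What is measured | Harm by arm? |
|---|---|---|
| Intervention (overview table) | Drug-class composite, QOL, individual drugs, perception, cost | No |
| Primary Objective | Change in prescription of the main classes | No |
| Subanalysis for each disease state | Initiation, dose composites, persistence | No (indirect only) |
| Secondary Objective | MMAS-4, PAM, KCCQ-12 | No |
| By Disease State | Therapy use, metabolic values, insulin dose, achieved doses, visit opportunities | No |
| Implementation Efficacy Measures; Mixed Methods Evaluation | Engagement, referral completion, timing, predictors of prescription | No |
| Statistical Methods (power) | Prescription rates | No |

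The nearest items are persistence and the dose composite, which can register down-titration. Neither records why a drug was stopped or reduced. Except for OAC, persistence is defined only for drugs already taken at baseline, so it misses the drugs that the interventions cause to be started.

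**2. Intensity of observation by arm (Research Methods)**

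- Arm A: education only.
- Arm B: adds prompts to clinicians about every two weeks and a patient-facing tool linked to the dashboard.
- Arm C: adds medication review by the virtual team every two weeks until optimisation is complete, on the same technology, with data that patient interviews may supplement.

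Statistical Methods makes A versus C the primary comparison, which is where observation differs most. The size of the difference is not known. A patient app also administers questionnaires in the trial generally, so arm A is not without contact.

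**3. The plan's own figure**

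The plan gives no safety calculation. Its efficacy figure is 121 per arm for 15% versus 30%, alpha 0.05, 80% power. With a two-sided test, pooled variance and mean rate 0.225:

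n = [1.96·√(2·0.225·0.775) + 0.842·√(0.15·0.85 + 0.30·0.70)]² / 0.15² ≈ 2.71 / 0.0225 ≈ 120.5, rounded up to 121. It reproduces.

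**4. What a safety comparison could show**

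Patients per arm: 750/3 = 250. With the stated 20–25% loss, 250·0.80 = 200 or 250·0.75 = 187.5, taken as 187.

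The event rates p below are assumptions, because the documents give none. The half-width of the 95% interval for a difference, with the same rate in both arms, is 1.96·√(2p(1−p)/n). The last two columns give the smallest increase detectable with 80% power at two-sided 0.05.

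| Assumed rate | Half-width, n=250 | Half-width, n=187 | Detectable, n=250 | Detectable, n=187 |
|---|---|---|---|---|
| 2% | 2.5 points | 2.8 | +5.3 | +6.5 |
| 5% | 3.8 | 4.4 | +7.0 | +8.4 |
| 10% | 5.3 | 6.1 | +8.8 | +10.4 |
| 20% | 7.0 | 8.1 | +10.9 | +12.8 |

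The two extremes written out: 1.96·√(2·0.02·0.98/250) = 0.025 and 1.96·√(2·0.20·0.80/187) = 0.081. At 200 per arm, power to distinguish an assumed 5% from 10% is about 48%.

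**The case against.** The strongest reply is that tabulating adverse events by arm is ordinary SAP content, and that the SAP is not at hand; Statistical Methods says it will be finalised before study completion. Data Sources does commit to capturing adverse events and to mapping 9 months of data in all three groups to pre-specified fields. Those fields are not listed, so hospitalisations may already be among them. This part stands: a reader might infer that safety cannot be assessed in this trial at all, and the document does not support that. It does not remove the point, because objectives and outcomes are set in the protocol and none here corresponds to the safety claim. A later SAP also could not make past collection uniform.

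A reader might also infer that arm C patients are seen every two weeks and that event counts are therefore not comparable. The protocol describes a medication review, not a patient contact; it ends once optimisation is complete, and patients stay in arm C even if the referral is never completed. Unequal ascertainment is possible, not established. Calling the capture passive would likewise be an inference, since the protocol describes no method of elicitation.

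Finally, this is an implementation trial of guideline-recommended care with all decisions left to clinicians, and the safety wording occurs in one sentence; the Primary Objective makes no such claim. That limits the severity but does not remove the mismatch.

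**Conclusion.** The point holds in a limited form. The protocol hypothesises safe optimisation and specifies no outcome that measures harm by arm, so the outcomes it specifies cannot answer that part. This rests on comparing the protocol's own sections and needs no outside figure.

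The primary comparison of prescription is untouched, and the change is recommended rather than essential. The absence of a monitoring board is not itself the defect; what is missing is a defined, uniformly collected comparison.

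A reader might expect an added outcome to establish safety. It would not. Under the assumed rates of 2–20% and 187–250 patients per arm, the half-width runs from about 2.5 to 8.1 points. That is enough to report an estimate with its uncertainty, but not enough to exclude moderate harm.

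**What to change.** Add one secondary safety outcome: all-cause hospitalisations and emergency visits over 9 months, drawn with the same fields and rules in all three arms from the EHR extract already planned under Data Sources. Report arm differences with 95% confidence intervals, and describe the result as an estimate.

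Keep clinician-coded adverse drug events descriptive only, because coding depends on how closely patients are observed and so has the same ascertainment weakness.

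If this is not wanted, delete the words *and safely* from the hypothesis under Research Question, Objectives & Aims.

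The first option costs a few more extract fields and will give wide intervals; the second costs a wording change. Neither alters randomisation, treatment or sample size.
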